7 Data Management	17
7.1 Clinical Site Data Management	17
7.2 Electronic Data Capture System	17
7.3 Study Monitoring	17
7.3.1 Site Monitoring Plan	18
7.3.2 Clinical Site Monitoring	18
8 Data Coordinating Center	18
8.1 Security and Confidentiality	19
8.2 Record Access	20
9 Bibliography	20

List of Tables

1 List of Peptides according to their function	11
2 Schedule of Events	13

1 Synopsis

Title	A Randomized, Double-blinded, Placebo-Controlled Study for the Treatment of Ocular Chronic GVHD with Processed Amniotic Fluid (pAF) Drops
Short Title	pAF for the treatment of Ocular GVHD
IRB Number	00103515
IND	18489
Phase	I/II
Design	This is a randomized, double-blinded, placebo-controlled study of the efficacy of pAF in patients with hematologic malignancies who have undergone Allogeneic Hematopoietic Stem Cell Transplantation (HSCT) and are diagnosed with chronic GVHD of the eye.
Study Duration	Two years
Study Center(s)	University of Utah
Objectives	
Primary Objectives:
 
 • To determine the safety of pAF in patients with chronic ocular GVHD. • To determine the clinical effects of pAF in patients with chronic ocular graft versus host disease. 
Secondary Objectives:
 
 • To determine the change in National Institutes of Health (NIH) Consensus Criteria (CC) ocular score of chronic GVHD at 30 ± 3 days, 60 ± 3 days, and 100 ± 3 days from baseline related to the administration of pAF. • To determine change in Functional Assessment of Cancer Therapy-General (FACT G) (Quality of Life (QOL)) at 30 ± 3 days, 60 ± 3 days, and 100 ± 3 days related to the administration of pAF. • To determine changes in visual acuity related to the administration of pAF. • To determine the effects of pAF on the corneal surface. • To determine the changes in dry eye symptoms using the grading provided by the International Dry Eye Workshop (DEWS) 2007 report.¹ • To determine the changes in patient reported pain level related to the administration of pAF using the 0–10 pain rating scale during the first 60 days of the study.

Continued on next page

Continued from previous page

Number of Subjects	15–20 patients
Diagnosis and Main Eligibility Criteria	
Inclusion:
 
 1. Patients diagnosed within 5 years after hematopoietic stem cell transplant for any disease, with any graft and any conditioning regimen with at least one of the following: 
 • Dry eye symptoms partially affecting (requiring lubricant drops > 3 × per day, punctal plugs, or thermally cauterized puncta) or significantly affecting (special eyewear to relieve pain) activities of daily living (ADL). • Unable to work because of ocular symptoms. • Loss of vision due to keratoconjunctivitis sicca (KCS). Patients may be using bilateral scleral lenses and/or bilateral punctal plugs at the time of accrual. 2. Patients who are 18 years of age or older. 3. Willing and able to provide informed consent. 
Exclusion:
 
 1. Patients who have any other reversible cause for dry eye at the time of accrual. 2. More than 3 lines of therapy beyond corticosteroids with or without calcineurin inhibitors or sirolimus. 3. Relapsed malignancy at time of accrual after the most recent transplantation. 4. A difference in dryness between both eyes of more than 2 points of the grading provided by the International Dry Eye Workshop (DEWS) 2007 report.¹ 5. Patients who are pregnant or plan to become pregnant while participating in the study. 6. Patients who are not willing to discontinue the use of any eye drops, with the exception of non-medicated lubricant eye drops (artificial tears). All eye drops (excluding non-medicated lubricant eye drops) must be stopped at least seven days before treatment with pAF. 7. Inability to comply with the investigational plan and visit schedule for any reason, in the judgement of the investigator.

Continued on next page

Continued from previous page

Study Product, Dose, Route, Regimen	
pAF will be given as one drop in 1 eye and saline (placebo) will be given in the other eye. pAF and placebo will be used in each eye twice daily, for a total of 30 days.
 
In patients wearing bilateral scleral lenses, the drops will be applied prior to lens insertion in the morning and immediately after removal at night

Statistical Methodology	
This is randomized, double-blinded, placebo-controlled study.
 
The clinical effects of pAF will be analyzed using descriptive statistics, Wilcoxon rank sum, and Fisher's exact test where applicable. Test for a significant response will be carried out using McNemar's test.
 
The proportion of subjects who experience adverse events and serious adverse events will be summarized descriptively; no inferential tests will be performed.

2 Objectives

Primary Objectives:

1. To determine the safety of pAF in patients with chronic ocular GVHD.
2. To determine the clinical effects of pAF in patients with chronic ocular GVHD.

Primary Endpoint:

1. Overall response (Complete Response & Partial Response) as defined in section 5.

Secondary Objectives and Endpoints:

1. To determine the change in National Institutes of Health (NIH) Consensus Criteria (CC) ocular score of chronic GVHD at 30 ± 3 days, 60 ± 3 days, and 100 ± 3 days from baseline related to the administration of pAF
2. To determine change in FACT G (QOL) at 30 ± 3 days, 60 ± 3 days, and 100 ± 3 days related to the administration of pAF.
3. To determine changes in visual acuity related to the administration of pAF.
4. To determine the effects of pAF on the corneal surface.
5. To determine the changes in dry eye symptoms related to the administration of pAF using the grading provided by the International Dry Eye Workshop (DEWS) 2007 report.¹
6. To determine the changes in patient reported pain level related to the administration of pAF using the 0–10 pain rating scale during the first 60 ± 3 days of the study.

3 Rationale and Background

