5.4 Concomitant Medications and Procedures

Only medications with ocular effects will be recorded at screening and at subsequent study visits. These medications will be recorded in the medical record and appropriate CRF.

Patients may use non-medicated saline eye drops (artificial tears), provided they are applied in both eyes greater than 30 minutes following the application of the study eye drops.

All other eye drops, other than non-medicated saline eye drops, are prohibited while the patient is on study. If the patient is on medicated eye drops, a seven day washout is required before starting treatment. Patients can enroll if they have bilateral punctal plugs or if puncta were previously thermally cauterized, but the insertion of punctal plugs or cauterization is not allowed while the subject is on study.

5.5 Assessment of Response:

Assessment of response will be performed at 30 ± 3 , 60 ± 3 and 100 ± 3 days after initiation of therapy with pAF. The response is a combination of the NIH CC assessments and the ophthalmologic assessment (DEWS evaluation) as follows:

- NIH Consensus Conference (CC) for assessment of response in chronic GVHD
- Ophthalmologic assessment: Dry eye assessment will be performed over the course of four eye exams, including a baseline comprehensive eye exam (including a dilated fundus examination), and three follow-up exams (without dilation) on Day 30 ± 3 , Day 60 ± 3 and Day 100 ± 3 . Signs and symptoms of dry eye will be assessed at each exam using the grading scale provided by the International Dry Eye Workshop (DEWS) 2007 report.¹ DEWS assessment will include visual symptoms, severity and frequency of discomfort, conjunctival injection, conjunctival staining (using NaFl), corneal staining (using NaFl), corneal/tear signs (including filamentary keratitis and debris), the eyelids and meibomian glands, and fluorescein tear break-up time (TFBUT). Each sign/symptom will be graded on a scale of 1 to 4, with 4 being most severe. A total score will be taken at each exam, and a cumulative decrease in overall score >2 will constitute improvement with treatment. Note: Schirmer testing will not be performed or graded, as it has no proven value in ocular chronic GVHD.

Responders would be defined as a one point improvement in the dry eye grading scale (DEWS), without worsening in the eye score (NIH Consensus Criteria Ocular Assessment).

5.6 Assessment of Secondary Endpoints:

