4 STUDY SUBJECTS AND ANALYSIS POPULATIONS

4.1 Eligibility

Patients will be eligible for enrollment if they meet all of the following inclusion criteria:

1. Patients with chronic GVHD \geq Grade II diagnosed within 3 years after hematopoietic stem cell transplant (HSCT) for any disease, with any graft, and any conditioning regimen with dry eye (patients may be using bilateral scleral lenses and/or bilateral punctal plugs at the time of accrual)
2. Patients who are 18 years of age or older.
3. Willing and able to provide informed consent.

Patients will be ineligible for enrollment if any of the following exclusion criteria are met:

- Patients who have any other reversible cause for dry eye at the time of accrual.
- More than 2 lines of therapy beyond corticosteroids with or without calcineurin inhibitors or sirolimus
- Relapsed malignancy after transplantation
- A difference in dryness between both eyes of more than 2 points of the grading provided by the International Dry Eye Workshop (DEWS) 2007 report
- Patients who are pregnant or plan to become pregnant while participating in the study.
- Patients who are not willing to discontinue the use of any eye drops, with the exception of non-medicated lubricant eye drops (artificial tears). All eye drops (excluding non-medicated lubricant eye drops) must be stopped at least seven days before treatment with pAF.
- Inability to comply with the investigational plan and visit schedule for any reason, in the judgement of the investigator.

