5.5 Derived and Computed Variables

The primary outcome for the study, response vs. non-response will be defined according to the following table.

Table 1: Response Table

Response Type	Definitions
Complete Response	Resolution of all manifestations of ocular GVHD 1. NIH CC eye score = 0 2. DEWS = 1
Partial Response (PR)	1. No worsening in NIH CC eye score 2. At least one point decrease in DEWS
Mixed Response	1a. Any decrease in the NIH CC eye score 1b. No improvement in DEWS. or 2a. Decrease in DEWS 2b. Worsening in the NIH CC eye score
No Response (NR)	No change in both the NIH CC score and the DEWS
Progressive Disease (PD)	Worsening on DEWS irrespective of NIH CC eye score

An eye will be coded as responding if it is categorized as CR or PR. All other situations, including MR, NR, and PD will be considered as not responding.

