6.2 Primary Outcome Analysis

6.2.1 Response Table

The outcome is the combination of two measures, the NIH CC criteria and DEWS. Each will be summarized at 30, 60, and 100 days.

The NIH CC is a four level ordinal score ranging from 0 to 3 with 0 being asymptomatic and 3 being the worst possible. Treatment and control eyes will be summarized at baseline and each visit using counts and percentages. At each visit we will summarize the number and percent of treatment and control eyes that have improved, stayed the same, and progressed compared to baseline. An improvement will be defined as movement to a lower score and symptom progression will be defined as movement to a higher score.

The DEWS is a four level ordinal score ranging from 1 to 4 with 1 being asymptomatic to mild and 4 being the severe. Similar to the NIH CC score, treatment and control eyes will

be summarized at baseline and each visit using counts and percentages. At each visit we will summarize the number and percent of treatment and control eyes that have improved, stayed the same, and progressed compared to baseline. An improvement will be defined as movement to a lower score and symptom progression will be defined as movement to a higher score.

Analysis of the primary endpoint will be coded as each eye having responded or not responded at the 30 day visit. Because a participant's eyes are more likely to be similar compared to eyes from two different participants we will conduct a paired analysis using McNemar's test, as implemented in PROC FREQ, by constructing the following table where A is the number of participants who had both eyes respond; B is the number of participants who responded in the active eye but not in the control eye; C is the number of participants who did not respond in the active eye but responded in the control eye; and D is the number of participants who did not respond in either eye. pAF will be deemed to be effective if B is significantly greater than its expected value. If the observed table from the trial is sparse we will utilize the exact version of the McNemar's test.

Table 2: Outcome Table

		Control Eye	
		Responding	Not Responding
Active Eye	Responding	A	B
	Not Responding	C	D

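### No minimum baseline DEWS grade per eye is visible, so an eye already at the floor of the SAP's scale can be randomized although it cannot show the one-point fall that most of the response definitions require

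*Protocol*

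**What the plan says.** **Entry.** The Protocol synopsis judges severity per person: symptoms affecting daily living, inability to work, or loss of vision. The first of these begins "Dry eye symptoms partially affecting (requiring lubricant drops > 3 × per day, punctal plugs, or thermally cauterized puncta". SAP 4.1 asks for a chronic GVHD grade and dry eye. Neither list gives a minimum DEWS grade for each eye. The one rule that compares the eyes excludes "A difference in dryness between both eyes of more than 2 points of the grading", and SAP 4.1 repeats it.

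**Scale.** SAP 6.2.1: "The DEWS is a four level ordinal score ranging from 1 to 4 with 1 being asymptomatic to mild". Protocol 5.5 describes something else: "Each sign/symptom will be graded on a scale of 1 to 4, with 4 being most severe", after which the items are totalled.

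**Response.** Protocol 5.5: "Responders would be defined as a one point improvement in the dry eye grading scale (DEWS), without worsening in the eye score". SAP 2.2.1 likewise asks for a DEWS decrease of at least one point for complete or partial response. In SAP Table 1 (section 5.5), partial response needs "At least one point decrease in DEWS" with no NIH worsening. Complete response in the same table is a state: NIH eye score 0 and DEWS 1, with no change from baseline mentioned.

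**Analysis.** The primary test is McNemar's on day 30 response in the ITT population (SAP 4.2.2 and 6.2.1). No rule covers eyes that start at the floor.

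**The concern.** A responder definition built on a one-point fall works only if every randomized eye has a point to lose. Per-patient symptom criteria do not ensure this, because the better eye of an unequal pair may sit at grade 1.

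McNemar's test draws its evidence from participants whose pAF eye responds while the saline eye does not (cell B of SAP Table 2). Where a fall is required, a participant whose pAF eye starts at grade 1 cannot enter that cell. The pAF response rate and the power then drop for a reason unrelated to pAF, in a pilot meant to supply preliminary efficacy data.

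The response table adds a second difficulty. A grade 1 eye whose NIH score falls to 0 is a complete responder under Table 1 but not under SAP 2.2.1 or Protocol 5.5. A grade 1, NIH 0 eye that never changes fits both the complete response row and the no response row.

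**Working it through.** **1. Which pairs are admitted.** On a 1-4 grade there are 4 × 4 = 16 ordered pairs. A difference above 2 removes (1,4) and (4,1), leaving 14. Five of these contain a grade 1 eye: (1,1), (1,2), (1,3), (2,1) and (3,1). This counts combinations and says nothing about how common they are.

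**2. The plan's own figures.** Inputs from Protocol 6 and SAP 7: alpha 0.05, control response 5%, treated response 60% with 15 participants or 50% with 19, power 80%. Two assumptions are added because the documents are silent: a two-sided test, and independent responses in the two eyes.

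- P(pAF only responds) = pT(1 − pC): 0.60 × 0.95 = 0.57, and 0.50 × 0.95 = 0.475.
- P(saline only responds) = pC(1 − pT): 0.05 × 0.40 = 0.02, and 0.05 × 0.50 = 0.025.
- With b and c the counts in cells B and C, the test favours pAF when b > c and 2 × P[Bin(b + c, ½) ≤ c] ≤ 0.05. Power is the total multinomial probability of such (b, c).

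Exact power is 85.3% for 15 participants and 83.1% for 19. The smallest numbers giving at least 80% are 14 and 19, so the stated 15 and 19 are reproduced within one participant.

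**3. Adding floor eyes.** Suppose k pairs have exactly one floor eye that cannot respond, with pAF assigned to either eye with probability ½. Such a pair has P(pAF only) = ½ × 0 + ½ × pT and P(saline only) = ½ × pC + ½ × 0. These are 0.30 and 0.025 in the first scenario, and 0.25 and 0.025 in the second. The remaining n − k pairs keep the probabilities of step 2.

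| k | n = 15, 60% vs 5% | n = 19, 50% vs 5% |
|---|---|---|
| 0 | 85.3% | 83.1% |
| 1 | 82.8% | 81.2% |
| 2 | 80.0% | 79.2% |
| 3 | 76.8% | 77.0% |
| 4 | 73.2% | 74.6% |

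The cost comes from floor eyes that receive pAF. If the one floor eye (k = 1) is known to be the pAF eye, power is 79.5% and 78.5%.

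**4. Dilution.** The expected pAF response rate is pT × (1 − k/2n). For k = 2 this is 60% × (1 − 2/30) = 56%, and 50% × (1 − 2/38) = 47.4%. For k = 4 it is 60% × (1 − 4/30) = 52%, and 50% × (1 − 4/38) = 44.7%.

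**The case against.** **Complete response stays open to a floor eye under Table 1.** This stands. A reader might infer that a grade 1 pAF eye can only be a non-responder, so that its participant must fall in cell C or D. That follows from Protocol 5.5 and SAP 2.2.1. Table 1 does not support it, because its complete response row needs no fall. The power figures therefore apply only where a fall is required.

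**The Protocol's DEWS is a total.** This also stands. Eight items are listed, so a simple sum would run from 8 to 32. On that scale a 2-point limit is a tight match, an eye at the minimum must be minimal on every item, and a requirement of at least 2 would exclude nobody. The scale has to be settled before an entry line can be written.

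**Floor eyes are probably few.** Inclusion selects symptomatic patients, whereas the SAP calls grade 1 asymptomatic to mild. With k = 1 power stays above 80%, and with k = 2 it is about the stated 80%. The Protocol allows up to 20 participants: at 50% response, 20 participants give 84.3%, 82.5% and 80.6% for k = 1, 2 and 3. A reader might infer that the trial is underpowered; without a value for k, the documents do not show that.

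**The planning rates may already include floor eyes.** The 5%, 50% and 60% are not tied to eyes with room to improve. If they describe all enrolled eyes, step 3 counts the loss twice.

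**Fuller eligibility text may exist.** The synopsis gives main criteria only, and the text between Protocol sections 3 and 5 was not in the copy reviewed. The SAP list has no such minimum, but it differs from the synopsis on other criteria, so it is only partial support.

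None of this supplies a per-eye minimum on the SAP's scale or removes the conflict within the response definitions.

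**Conclusion.** The point holds as a cheap improvement. On the SAP's 1-4 grade, the eligibility text available lets an eye at grade 1 be randomized and kept in the ITT analysis, although it cannot make the fall that Protocol 5.5, SAP 2.2.1 and the partial response row require. The missing per-eye minimum is the cause; the 2-point allowance between eyes only widens the route.

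Under the assumptions of steps 2 and 3, the loss of power is about 2 to 3 percentage points for one such pair (85.3 − 82.8 = 2.5; 83.1 − 81.2 = 1.9). For four pairs it is about 8 to 12 points (85.3 − 73.2 = 12.1; 83.1 − 74.6 = 8.5). The number of such pairs is unknown and probably small. A reader might also infer a risk of false positive findings. The design does not support that: which eye gets pAF is random, so type I error is not inflated.

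**What to change.** 1. State one DEWS scale for both eligibility and response, reconciling the SAP's 1-4 grade with the totalled item score in Protocol 5.5.
2. On that scale, require each eye's baseline to be at least one point above the minimum (grade 2 or above on the 1-4 grade). Put the same line in both documents. If the reconciled response rule asks for a larger fall, the margin should match it.
3. Make complete response in SAP Table 1 also require a DEWS fall from baseline, as SAP 2.2.1 already says. Once item 2 is in force, an eye that reaches grade 1 has necessarily fallen, so this matters mainly for eyes randomized before the change.
4. If any floor eye has already been randomized, keep it in ITT and add a supportive McNemar analysis limited to participants with both eyes above the floor at baseline.

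The cost is one eligibility line, one amended table row and, if needed, one extra analysis. The baseline DEWS examination is already scheduled. The downside is a few more screen failures. Before amending, check the Protocol's full eligibility section for a per-eye minimum.

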3.1 Chronic GVHD

Allogeneic (Allo) Hematopoietic Stem Cell Transplantation (HSCT) is a potentially curative treatment modality for patients with hematologic malignancies who would otherwise have a poor outcome with other conventional treatment approaches alone. Allo HSCT causes donor-derived immune responses that can result in the desired graft-versus-tumor effect as well as the undesired complication, Graft versus Host Disease (GVHD). Chronic GVHD is the main complication for long-term survivors of a successful AlloHSCT. Chronic GVHD occurs in more than 50% of all patients who undergo an allo HSCT and the majority of patients who develop acute GVHD as a complication of their allo HSCT. Chronic GVHD can involve multiple organs and require prolonged immunosuppressive therapy. Advanced chronic GVHD is typically manifested by significant fibrous tissue deposition in different organs, leading to disabling symptoms, most commonly because of sicca syndrome and sclerodermatous forms of the disease. Sicca syndrome can lead to severe pain, visual impairment, and mucositis leading to malnutrition. Sclerodermatous chronic GVHD can cause dramatic limitations in the range of motion, with different degrees of immobility, and occasionally restrictive pulmonary disease. At this stage, current treatment strategies are almost always ineffective, at least in part due to the irreversibility of manifestations related to fibrosis. The mainstay of first-line immunosuppressive therapy in patients with chronic GVHD is systemic glucocorticoids and there are no standard second-line therapies. Systemic glucocorticoids have limited efficacy and significant long-term complications. Despite the many alternative immunosuppressive agents to systemic glucocorticoids, no single class of immunosuppressive agents has persistently produced a steroid-sparing effect in patients with chronic GVHD.²⁻⁸ In conclusion, chronic GVHD and its current standard therapy have a major negative impact on the quality of life (QOL) and survival in patients in whom allo HSCT was able to achieve a cure from their original hematologic malignancy. Therefore, there is a desperate need for more effective agents in treating chronic GVHD.

Ocular GVHD in particular affects more than half of the patients within 2 years of the diagnosis of chronic GVHD.^{9, 10} The fibroproliferative nature of ocular chronic GVHD makes it irreversible in its advanced stages, and at this point systemic therapies are ineffective. Thus, the management is supportive, through control of surface inflammation, lubrication, control of drainage and evaporation.¹¹ Despite some advances in the area of supportive care, such as scleral lenses that effectively control evaporation, the problem of ocular chronic GVHD is far from resolved and it is still associated with worse overall health-related quality of life.¹⁰

